#### Antithrombotic Drugs to Prevent Post Stroke DVT

Both low and medium dose subcutaneous heparin reduce the risk of DVT, and probably PE, in patients with acute ischaemic stroke (Gubitz et al 2000). However, evidence from the International Stroke Trial (IST 1997) shows that even low dose heparin (5,000 unit twice daily) is associated with a significant excess of symptomatic intracranial and extracranial bleeds which offset any other advantages heparin may have on recurrent ischaemic stroke and fatal PE. Trials have demonstrated that aspirin is probably effective in preventing DVT and PE after surgery (The Antiplatelet Trialists' Collaboration 1994, Pulmonary Embolus Prevention Trial 1999). The results of the IST and the Chinese Acute Stroke Trial (CAST) suggest that aspirin should be started in all patients with a proven ischaemic stroke as soon as possible since it is associated with a reduced risk of death and recurrence within the first month (Gubitz et al 2000). Therefore all patients with stroke, except those with haemorrhagic stroke or with other contraindications to aspirin, should be treated with aspirin. This might also be expected to reduce the frequency of DVT and PE. Indeed in the IST, although DVT was not an endpoint, aspirin was associated with a reduction in risk of PE in the first two weeks from 0.8% to 0.6% (2p = 0.08, odds reduction 26% (95% CI 48% reduction to 4% increase) IST 1997).

#### The Role of Graduated Compression Stockings

#### Rationale

GCS are thought to reduce the risk of DVT by:

- Compressing the leg and thus reducing the cross sectional area of the veins which in turn reduces stasis by increasing the blood flow velocity.
- Increasing flow by providing greater compression around the ankle than more proximally.
- Augmenting the effect of the calf muscle pump.
- Improving the function of venous valves and reduction of venous pooling.
- Altering levels of clotting factors.

Therefore, almost all of the randomised evidence to support the use of GCS comes from peri-operative patients. It does not seem reasonable to extrapolate the results of the systematic review in surgical patients to those with stroke. In surgery, stockings are applied before the operation, which represents a brief insult to the veins in the legs. Paralysis only occurs during the surgery itself and immobilisation is usually only for a few days. In stroke, stockings are applied after the onset of paralysis and the patients are often immobile for weeks. They may have prolonged paralysis of the affected leg. Paralysis may reduce the effectiveness of stockings in augmenting flow. Moreover, many stroke patients develop DVT and PEs several weeks after the ictus (Cope et al 1973, Oczkowski et al 1992).

#### The Problems Associated With GCS In Stroke Patients

The risks of GCS are small. However, in patients with severe peripheral vascular disease and/or peripheral neuropathy, their use can cause skin necrosis and occasionally this has necessitated amputation (Kay and Martin 1986, Merrett & Hanel 1993, Warlow et al 1996). Patients with stroke are more likely than surgical patients to have diabetes and peripheral vascular disease. Perhaps more significant than this small risk is the much more common experience of patients and nursing staff that GCS, especially the full length variety, are uncomfortable and may be difficult to apply in patients with limb weakness. In addition, many stroke patients are incontinent of urine and /or faeces, which can lead to soiling of the stockings, greater discomfort and more problems with the underlying skin. If stockings are ineffective the nursing staff's time applying and monitoring them might be put to better effect.

In the UK graduated compression stockings vary in cost, from £4 to £7 for one pair of full length stockings. In some other countries the cost of stockings are much higher. A patient might need two pairs per month allowing for regular washing. In addition there are staff costs relating to training in their use and, the regular application and removal of stockings in immobile patients. Therefore, given the frequency of stroke the financial implications of routine use of GCS are important.

#### Variation in use

In a recent survey (Ebrahim and Redfern 1999) (with a response rate of 86.8%) of over 1,716 physicians in the UK who routinely care for stroke patients, 46% thought stockings were useful for prevention of post stroke DVT, 26% thought they were of no use and 28% were uncertain of their value. If these views are translated into everyday practice it is clear that there is considerable variation in how patients are treated. This variation must be unacceptable if stockings are effective (since perhaps as many as 50% of patients are currently denied them) or ineffective (since this represents a huge waste of resources). It is clear therefore that we need to perform a large randomised trial to establish the effectiveness (or not) of GCS in prevention of DVT and PE after stroke.

There is wide variation in the length of stockings used which partly reflects the greater practicality and comfort of the below knee stockings despite the lack of definite evidence of benefit. There is a clear need for further studies to establish whether below knee stockings are effective in prevention of DVT and PE in all patients at risk, including those with stroke.

#### **Detecting Deep Venous Thrombosis**

The lack of recent studies of post stroke DVT and trials to evaluate preventative treatments is in part due to the absence of a sensitive, specific, safe and practical test to diagnose DVT (Anand et al 1998). Options include: venography, radio-labelled fibrinogen scanning, Doppler ultrasound, plethysmography, magnetic resonance imaging and the measurement of D-Dimers in the blood or plasma. None represents an ideal technique on which to base ones primary outcome in a randomised trial of DVT prevention.

**Venography** is still regarded as the gold standard with which other techniques are compared. However it is invasive, is occasionally associated with serious adverse reactions to the contrast and problems with interpretation arise where there is inadequate filling of veins. One might expect 10% of tests to be technically inadequate. In this trial where we are expecting only perhaps 10% of patients to have a DVT it is probably unreasonable to subject the other 90% to such an invasive and uncomfortable test for no gain. Its use is likely to be associated with difficulties in obtaining informed consent, low accrual and a high drop out rate especially as we plan to screen over the first month after randomisation.

**Radiolabelled fibrinogen** provided a very sensitive and reasonably specific test for identifying calf vein DVT although it was less specific for more proximal and more clinically relevant thromboses. Because it appeared to be reasonably safe it was used to screen asymptomatic patients in earlier studies. Unfortunately, because of concerns about the transmission of virus particles via blood products it is no longer available.

**Doppler ultrasound** imaging provides a very accurate and specific tool to detect above knee thrombus in symptomatic patients. There is more uncertainty concerning its sensitivity and specificity for detecting calf vein thrombus and in asymptomatic patients (Davidson 1998). Reported sensitivities in asymptomatic patients vary between 42% and 70% with positive predictive values varying between 35% and 83% depending on the operator's expertise and the prevalence of DVT in the patient group examined. However, it is rapidly becoming the investigation of choice to confirm the diagnosis of DVT since it is non invasive (Baxter 1997). It is acceptable to patients, can easily be repeated several times and uses equipment which is widely available. Thus consent, accrual and compliance in a trial are likely to be more easily achieved than with alternatives.

**Plethysmography** This technique is of comparable accuracy to Doppler ultrasound and is also non invasive but it is not widely available in centres which are likely to participate in this randomised trial.

**Magnetic Resonance Imaging** Preliminary reports suggest that this technique might offer an alternative non invasive method of detection. However it is available in very few centres and has not yet been fully evaluated (Moody 1997, Kelly et al 2001).

**D-Dimers** are degradation products produced when thrombus present in the circulation is lysed. Raised levels of D-Dimers have been used as a very sensitive but less specific test for diagnosis of DVT (Bounameaux et al 1997). However, its performance in detecting DVT/PE in prevention studies remains to be established. At this time it could not be used as a test to confirm DVT, but given its sensitivity it might be used as a preliminary screening test to select patients for imaging (Harvey et al 1996, Bernardi et al 1998)

#### **Primary Research Questions**

The primary research questions are:

- Does early and routine application of above knee or full length graduated compression stockings reduce the risk of above knee DVT in the weeks following an acute stroke?
- Are above knee or full length graduated compression stockings more effective than below knee graduated compression stockings in reducing the risk of DVT?

#### Secondary Questions

- What is the frequency of Doppler ultrasound proven DVT in immobile stroke patients treated routinely with antiplatelet agents?
- What clinical factors might predict a greater risk of post stroke DVT?
- Are GCS effective in preventing DVT in the non-paralysed leg in stroke patients which would provide data relevant to patients immobilised with other medical conditions?

#### Add on Studies

In addition, we would ideally aim to collect extra data in selected centres, which would allow us to answer some additional questions:

- Can haematological investigations refine the clinical prediction of which patients will develop post stroke DVT and other vascular events?
- What is the sensitivity and specificity of D-Dimers (measured using an ELISA test) in the detection of DVT after stroke?
- What is the inter-observer reliability of Doppler ultrasound scanning in the detection of above and below knee DVT after stroke?
- What is the sensitivity and specificity of MRI in the detection of DVT after stroke?
- How acceptable are graduated compression stockings to patients?
- What are the resource implications of the routine use of stockings?
- What are the genetic markers of increased risk of post stroke DVT?

#### Trial Design – A Family of Trials

CLOTS is a family of two multicentre randomised controlled trials with blinded assessment of primary outcomes (Dennis et al 1999). The two trials will make use of common randomisation, data collection and follow up systems. Centres will generally randomise patients into either Trial 1 or Trial 2 depending on their current practice and beliefs with respect to graduated compression stockings after stroke.

#### Trial 1

In centres where collaborating clinicians / nurses are uncertain about the value of graduated compression stockings in stroke patients, patients will be allocated to one of the following two treatments:

#### Full length graduated compression stockings in addition to routine care

Or

#### Routine care and avoid the use of graduated compression stockings

If allocated to full length GCSs, these should be applied to both legs as soon as possible after the randomisation phone call and should be worn until the patient is independently mobile around the ward (i.e. can get up from a chair/ out of bed and walk to the toilet without the help of another person), or until the patient is discharged from hospital or until the patient declines to wear them. In the last case, below knee stockings should be substituted if the patient will accept them.

If allocated to routine care, full length and below knee GCS should be avoided unless a clear indication for their use becomes obvious.

#### Trial 2

In centres where responsible clinicians / nurses are certain about the value of GCS in stroke patients but are uncertain whether to use full length or below knee stockings patients will be allocated to one of the following two treatments:

#### Full length graduated compression stockings in addition to routine care

Or

#### Below knee graduated compression stockings in addition to routine care

The appropriate length of GCS, should be applied to both legs as soon as possible after the randomisation phone call and should be worn until the patient is independently mobile around the ward (i.e. can get up from a chair/out of bed and walk to the toilet without the help of another person) or until they are discharged from hospital or until the patient declines to wear them.

#### **Routine Care**

In Trial 1 and 2, all patients should receive aspirin as soon as a haemorrhagic stroke has been excluded by CT as long as there is no other contraindication. The responsible clinician may prescribe aspirin before a CT scan where this is accepted practice in patients thought unlikely to have a haemorrhagic stroke. In some centres heparin may be used (despite the lack of evidence of overall benefit). In these centres use of heparin must be the same in both treatment groups.

#### **Inclusion Criteria**

• Any patient admitted to hospital within 7 days of a clinical stroke fulfilling the WHO criteria

and

 Who is not able to get up from a chair/ out of bed and walk to the toilet without the help of another person

and

• In whom the responsible clinician / nurse is substantially uncertain about either the value of graduated compression stockings (Trial 1) or the optimal length (Trial 2).

Patients can be randomised from Day 0 (day of admission) to Day 3 of hospital admission. If a patient has a stroke during a hospital admission they are eligible until Day 3 from the stroke onset (Day 0).

#### **Exclusion Criteria**

- Patients who, in the opinion of the responsible clinician / nurse, are unlikely to benefit from GCS.
- Patients with peripheral vascular disease, diabetic or sensory neuropathy, where the responsible clinician / nurse judges that stockings may cause tissue necrosis.

#### Consent

UK Multicentre Research Ethical Committee (MREC) approval has been granted. Each collaborating centre will need to confirm Local Research Ethics Committee (LREC) approval.

Patients (or their carers) are given a Patient Information Booklet which describes the aims of the trial and the potential risks and benefits of graduated compression stockings. The patients (or their carers) should be given enough time to consider the trial fully and ask any questions they may have about the implications of the trial.

Patients are asked for their written informed consent unless they are unable to do so because of reduced conscious level, cognitive or communication problems. In these cases the randomising clinician or nurse can either gain witnessed verbal consent or assent of the patient's next of kin. Randomisation without patients' consent or relatives' assent is not permitted in the UK but is allowed in other countries where randomisation without patients' or relatives' agreement is permitted by law and where this has been agreed by the local ethics committee. In such circumstances the agreement of the patient and or relative should be sought when this becomes practical.

#### **Randomisation Procedure**

The randomising clinician or nurse collects baseline data necessary to complete a randomisation form. He/she then rings a telephone randomisation service, giving the baseline data (which are then stored securely) and receives the treatment allocation at the end of the call. A minimisation program is used to achieve optimum balance for important prognostic factors i.e.

- Delay since stroke onset. (Day 0 or 1 vs. Day 2-10)
- Stroke severity (using a validated prognostic model (Counsell 1996) which includes the following factors; age, pre stroke dependency in activities of daily living, living with another person prior to stroke, able to talk and orientated in time, place and person, and able to lift both arms to horizontal position against gravity).
- Severity of leg paresis (able or not to lift leg off the bed)
- Use of heparin, warfarin or thrombolysis (rt-PA) at the time of enrolment
- Centre

By balancing randomisation within centres we should avoid problems associated with variation in accuracy of Doppler ultrasound between centres.

#### Follow up

Patients should have a Doppler ultrasound examination of the veins in both legs between Day 7 and Day 10 and between Day 25 and 30. This examination will document thrombus in the calf, popliteal and femoral veins separately. Centres are prompted to perform this test by fax or email sent by the trial management system.

Where the randomising person judges that it is likely to be impractical to perform a Doppler ultrasound between Days 25 and 30, they may, prior to randomisation, stipulate that a Doppler ultrasound will only be performed between Days 7 and 10. This might be the case if the patient is likely to be discharged home to

another region or transferred to a rehabilitation facility that does not have use of Doppler ultrasound facilities and is remote from the randomising centre.

Stockings should be removed before the patient leaves the ward to have the Doppler ultrasound to ensure optimal blinding of the primary outcome measure (sufficient time needs to be allowed to let indentations due to compression stockings disappear). The Doppler ultrasound operator will be asked to guess which treatment group the patient is in prior to the examination to estimate the effectiveness of blinding. Thus patients enrolled in CLOTS will benefit from non invasive screening for DVT which is likely to lead to earlier and probably more effective treatment and prevention of PE.

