#### Management of DVT in the Trial

A Radiology Report Form should be completed for all Doppler ultrasounds and venograms. This form, and in the case where there is evidence of DVT, the best image, still or video, should be returned to the CLOTS Co-ordinating Centre in Edinburgh.

If a popliteal or femoral vein DVT is detected during the routine Doppler ultrasound examinations, the responsible clinician will need to decide whether to confirm the presence and extent of any thrombus using venography. Although they may only perform confirmatory venography where the Doppler ultrasound is equivocal in their normal practice, compared with treating patients with a swollen leg the positive predictive value of a screening Doppler ultrasound study performed in an asymptomatic patient is likely to be lower. Put another way, the Doppler result is more likely to produce a false positive result in an asymptomatic patient. If the clinician is satisfied that the patients has a DVT (with or without a confirmatory venogram) the patient should be anticoagulated using subcutaneous heparin according to local protocols as long as there is no contraindication (SIGN Guidelines 1999).

If only calf vein thrombus is detected (by screening Doppler ultrasound and/or venography), the responsible clinician may anticoagulate the patient according to local protocols or alternatively arrange a follow up Doppler ultrasound approximately seven days later to identify any propogation into the popliteal vein. If definite popliteal or femoral vein thrombus is detected the patient should be anticoagulated unless contraindicated. If calf vein thrombus is detected during the first scheduled scan (between Day 7 to 10) a scan should also be performed between Days 25 and 30 in addition to any other scans deemed necessary.

If a patient develops symptoms or signs suggestive of DVT during their admission they should be investigated by either Doppler ultrasound and/ or venography and treated according to local protocols if the diagnosis is confirmed. Such patients should still have a Doppler ultrasound between Day 25 and 30 blinded to treatment allocation.

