#### Sample Size

Ideally the trial would demonstrate the impact of graduated compression stockings on survival and functional status. However, this would require a trial of enormous sample size. We have therefore chosen a surrogate outcome as our primary outcome, i.e. presence of first symptomatic or asymptomatic DVT in the popliteal or femoral veins detected on either of two routine Doppler ultrasound scans (performed at about 7-10 days and 25 – 30 days) or contrast venography within 30 days of randomisation.

In this trial we have elected to define our sample size not in terms of the number of patients we plan to enrol but rather the number of primary outcomes we need to detect. To achieve at least 90% power in Trials 1 & 2 we need to identify about 175 and 300 patients with our primary outcome in each trial respectively. This might be achieved by enrolling 1500 and 3000 patients in Trials 1 and 2 respectively, if thrombus will be detectable in the popliteal or femoral veins within 30 days of randomisation in 15% of control patients, 9% of those wearing full length GCS and 13% of those wearing below knee stockings. If the current event rate in our pilot phase applies we may require about 2000 and 3500 in Trials 1 and 2 respectively.

The estimates of treatment effects are based on the systematic reviews and the prevalence of DVT detected on Doppler ultrasound in stroke patients estimated from a previous RCT (Muir et al 2000), an observational study (Oczkowski et al 1992) and our start up phase. A recent (Dec 2002) confidential review (by the trial statistician) of the event rates in the CLOTS start up phase(for all treatment groups combined) for the first 160 patients followed up to 30 days indicated that about 8% of patients had our primary outcome.

These sample sizes take into account: the uncertainty introduced by the 70% sensitivity and 97% specificity of Doppler ultrasound in identifying DVT in mainly asymptomatic patients; an attrition rate due to death (8% in our start up phase) and missing Doppler results (8% in our start up phase) in the first month; the anticipated low non – compliance rate.

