#### Thank you for randomising this patient.

Appendix 6 Radiology Report Form Appendix 6 Radiology Report Form **CLOTS/RRF/V1** 

1.

2.

For office use

CLOTS/RRF/

Please complete and return by fax to the CLOTS Co-ordinating Centre on [name]

Hospital Number: or H	ospital Name _			
Patient ID:		Patient Ir	nitial:	
Procedure performed today	Doppler	Venog	graphy 🗆	Both
Date(s) procedure performed	Doppler	_//	Venography _	//
Did this patient attend wearing sto	ockings?	Yes 🗆	No 🗆	
Results - Any D.V.T. evident?		Yes 🗆	No 🗆	
Kanna DVT www.aant.wlaass.aa				

If any DVT present please send best still picture that demonstrates this to the CLOTS Co-ordinating Centre (address below).

If Yes:		Right Leg	Left Leg	
Femoral:	Yes, definite			
	Yes, probable			
	None			
Popliteal:	Yes, definite			
	Yes, probable			
	None			
Calf:	Yes, definite			
	Yes, probable			
	None			
	Veins Not Visualised			

We need to know if you are aware of whether the patient has been wearing compression stockings – this will tell us how "blind" you are to the treatment allocation

Do you think this patient has been wearing compression stockings (Do not ask the patier	ıt!)? Yes □	No 🗆	No Idea 🛛	
If yes, which length? Form completed by:	Full length	Below knee		

Thank you for completing this form, now please fax or post it to the

CLOTS Co-ordinating Centre, Neurosciences Trials Office Western General Hospital, [name] [contact]

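### The protocol asks the Doppler operator to guess the allocation before scanning, but the report form collects the guess after the DVT result, so the blinding check is open to influence from the outcome

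*Protocol*

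**What the plan says.** The Follow up section of the protocol is explicit about timing: "The Doppler ultrasound operator will be asked to guess which treatment group the patient is in prior to the examination". The same sentence gives the reason, which is to estimate the effectiveness of blinding.

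The guess is collected on the Radiology Report Form (Appendix 6). Management of DVT in the Trial sets the form's scope: "A Radiology Report Form should be completed for all Doppler ultrasounds and venograms". Its items run in this order:

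1. "Procedure performed today", with the date
2. Whether the patient attended in stockings
3. "Results - Any D.V.T. evident", then femoral, popliteal and calf findings for each leg
4. An explanatory line, "We need to know if you are aware of whether the patient has been wearing compression stockings"
5. The guess, "Do you think this patient has been wearing compression stockings", with the answers yes, no or no idea, and the stocking length if yes
6. The line for the person completing the form

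The only instruction attached to the guess is not to ask the patient. No other form in the protocol records it.

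**The concern.** Stockings are visible on the ward, so these trials depend on blinded scanning. Trial Design describes the assessment of primary outcomes as blinded. Secondary Outcomes accepts that detection of symptomatic DVT is not blinded and adds an analysis without those events. The guess is the protocol's own check that blinding of the scan held.

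A guess made before the scan can reflect only cues about the allocation. A guess made after the scan can also reflect what was found: an operator who believes stockings work may infer no stockings from a thrombus. The answer then mixes failed blinding with inference from the outcome, and nothing on the form allows the two to be separated later.

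**Working it through.** **Text comparison.** Follow up requires the guess before the examination. The form is worded for a procedure already performed and prints the guess after the results. It neither asks for an earlier answer nor records when the answer was given. A completed form therefore cannot show whether the Follow up instruction was met.

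**Size.** The protocol states no figure for this check, so there is none to reproduce. What follows is an illustration.

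Inputs from Sample Size: "15% of control patients, 9% of those wearing full length GCS and 13% of those wearing below knee stockings".

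Assumptions, not in the protocol: arms are equal in size; operators are fully blind; without a DVT they guess 50/50; after seeing a DVT they name the arm expected to do worse with probability q. A value of q = 0.5 means the result has no influence, which is the position when the guess precedes the scan.

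For an arm with DVT rate p:

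- Probability of naming the worse arm: g = p·q + (1 − p)·0.5
- Overall proportion correct: [g(worse arm) + 1 − g(better arm)] / 2
- DVT rate among those guessed to be in the worse arm: p·q / g
- DVT rate among those guessed to be in the better arm: p·(1 − q) / (1 − g)

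*Trial 1 (control 15%, full length 9%), q = 1.* Control: g = 0.15 + 0.85 × 0.5 = 0.575. Full length: g = 0.09 + 0.91 × 0.5 = 0.545. Correct: (0.575 + 0.455) / 2 = 51.5%.

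*Trial 1, q = 0.75.* Control: g = 0.1125 + 0.425 = 0.5375. Full length: g = 0.0675 + 0.455 = 0.5225. Correct: (0.5375 + 0.4775) / 2 = 50.75%.

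DVT rates by guess in Trial 1:

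| q | Control, guessed control | Control, guessed stockings | Stockings, guessed control | Stockings, guessed stockings |
|---|---|---|---|---|
| 0.5 | 15% | 15% | 9% | 9% |
| 0.75 | 0.1125/0.5375 = 20.9% | 0.0375/0.4625 = 8.1% | 0.0675/0.5225 = 12.9% | 0.0225/0.4775 = 4.7% |
| 1 | 0.15/0.575 = 26.1% | 0% | 0.09/0.545 = 16.5% | 0% |

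Among wrong guesses, the control v stockings comparison moves from 15% v 9% to 8.1% v 12.9% (q = 0.75) or 0% v 16.5% (q = 1), so a real benefit appears reversed. Among correct guesses it becomes 20.9% v 4.7% (q = 0.75), so the benefit is exaggerated. No operator in this illustration was unblinded.

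*Trial 2 (below knee 13%, full length 9%).* At q = 1, g is 0.565 and 0.545, and correct guesses are (0.565 + 0.455) / 2 = 51.0%. At q = 0.75 they are 50.5%. The below-knee DVT rate by guess is 18.3% v 7.0% (q = 0.75) or 23.0% v 0% (q = 1).

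**The case against.** **Form order is not completion order.** The form does not say to answer last, and Follow up says to answer first. This stands in part. A reader might infer that the guesses are contaminated; the documents show only that they can be, and that nobody could tell afterwards which ones were.

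**The usual check barely moves.** This stands. With 1500 patients and one guess each, the standard error of the percentage correct is √(0.25/1500) = 1.3 points, so 51.5% lies about 1.2 standard errors from chance. If the roughly 8% pooled start-up rate applied in the same ratio (10% v 6%, an assumption), the figure would be 0.08 × 0.625 + 0.92 × 0.5 = 51.0%. A reader might instead point to the share of DVT-positive patients guessed correctly, 0.15 / (0.15 + 0.09) = 62.5%. That holds only under the extreme rule q = 1 and only for the 12% of patients with a DVT, so it does not measure the overall effect.

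**The protocol states no analysis of outcome by guess.** True, so the large distortion in the table is conditional on someone making that comparison.

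**Other safeguards exist.** Stockings come off before the patient leaves the ward, time is allowed for marks to fade, and the form asks ahead of the results whether the patient arrived in stockings. These protect the scan and capture the most obvious route of unblinding. They do not establish when the guess was made.

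**The illustration is simple.** It applies 30-day patient-level rates as if there were one scan per patient, and it ignores the no-idea answer. It shows direction and rough size only.

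**Conclusion.** The Follow up section and Appendix 6 disagree on when the guess is made, and the form as printed leaves the blinding check open to influence from the scan result. The damage is limited to that check. Under the stated assumptions, overall correct guesses rise by at most 1.5 points in Trial 1 and 1.0 point in Trial 2. Any comparison of DVT rates by guess could be badly distorted, even reversed, and the pattern could not be distinguished from biased reading.

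A reader might infer that the primary outcome is biased or the trial result discredited. The documents do not support that: the order of questions on a form does not alter what the operator sees in the veins. This is an inconsistency worth correcting because the correction is easy and the timing of a guess cannot be recovered later.

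**What to change.** Move the guess (stockings yes, no or no idea, and length) above the results block of the Radiology Report Form and mark it *complete before scanning*. The form then matches the Follow up section. The cost is a new version of a one-page form; patients, scans and sample size are unaffected. Guesses already collected on the current form cannot be re-timed, so the change is best made early.

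The problem should not be met with a sensitivity analysis restricted to patients who arrived without stockings and whose guess was wrong or no idea. Arriving in stockings is largely confined to the stocking arm in Trial 1, and guesses may follow the appearance of the legs. Such a restriction selects on post-randomisation features that differ by arm and departs from the intention-to-treat basis set under Analyses.
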